4. STUDY AIMS AND OBJECTIVES

This study will be delivered in two sections: Part A and Part B. The aim of Part A is to assess whether intensive home monitoring of creatinine is an acceptable and feasible form of monitoring for patients. Part B of the study will aim to show earlier detection of deteriorating kidney function and AKI as compared to standard of care renal monitoring.

Table 2: Study objectives, outcomes and measures

Objectives	Outcome Measures	Timepoint(s) of evaluation of this outcome measure (if applicable)
Primary Objectives		
Part A: To evaluate patient acceptance of intensive home-monitoring of whole-blood creatinine.	Questionnaire and interview Absolute number of creatinine readings received-expected vs actual Time sample taken vs. time expected to take Value sent/received vs. value on device (when downloaded at the end of the study period)	Week 4
Part B: To evaluate the potential for earlier diagnosis of AKI/change in renal function with intensive home-monitoring of whole-blood creatinine.	Time from beginning of current cycle treatment to detection of AKI by amended algorithm or clinician/laboratory reading Severity of AKI at detection (as	Throughout study period
	per Kidney Disease Improving Global Outcomes AKI Work Group staging) Overall change in renal function from beginning to end of study period	

Secondary Objectives		
Part B: To assess whether intensive monitoring influences the change in kidney function over the study period compared to standard of care	Comparing kidney function at the beginning and end of the study	Weeks 1 and 6
Part B: To assess whether home monitoring of kidney function has a positive impact on a patient's quality of life.	Medical outcomes study short form 36 (SF-36) questionnaire	Week 6
Part B: To evaluate the adherence of patients to intensive home monitoring regimen	Absolute number of creatinine readings received Time sample taken vs. time expected to take Value sent/received vs. value on device (when downloaded at the end of the study period)	Week 6
Exploratory Objectives		
Part A: Using data gathered to improve and test amended AKI algorithm	Amended algorithm outcome vs clinician assessment Feedback and analysis from interviews and questionnaires	On completion of Part A
Part B: To explore the value of novel renal biomarkers in the cancer population for early detection and monitoring of AKI.	Urine and serum analysis	Throughout study period

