5.2 Part B

If, following Part A, the process is found to be an acceptable form of monitoring to patients, the study will continue to Part B. This will evaluate the potential for earlier diagnosis of AKI with intensive home monitoring of kidney function (plus standard of care monitoring) compared with standard of care only. The decision of whether to proceed to this stage of the study is described in further detail below. Participants who have been recruited to Part A of the study can continue to Part B if they so wish (and will be randomised).

Part B will enrol 60 patients being treated for cancer with potentially nephrotoxic anti-cancer therapies, randomised to either the intensive monitoring (device) group or the standard of care monitoring group, in a 1:1 ratio. Participants in both groups will be asked to complete a quality of life questionnaire at baseline. Both groups will receive standard of care monitoring of kidney function. In addition, participants in the intensive monitoring group will upload their creatinine reading three times per week (Mon/Wed/Fri) for 6 weeks. As in Part A, participants in the intensive monitoring group will be required to access the app on their own compatible device and upload their readings over their own internet connection. In both study arms, in line with scheduled clinic appointments (weeks B1, B3 and B6), blood and urine will be collected for exploratory biomarker analysis, along with renal function and cystatin C. When a participant attends a clinic appointment, a creatinine reading will be taken (either by the study participant or by a member of the study team) using the device, for comparison with the laboratory reading of creatinine taken that day.

During Part B of the study, when a participant has submitted their creatinine reading they will receive a successful submission message on the app and may receive feedback based on their reading (this depends on feedback from Part A of the study, performance of the amended algorithm from Part A and development of the smart phone application). As with Part A, participants will be directed to their

parent medical team if there is concern over their reading. Creatinine readings and AKI alerts from the algorithm will also be reviewed by the Chief Investigator once a week and highlighted to the parent medical team if there are concerns.

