At the end of Part B, all participants in both groups will be asked to complete a quality of life questionnaire, and those in the intensive monitoring arm will also be asked to take part in a short interview and complete a questionnaire reviewing the process of home monitoring and sending in creatinine results, (as in Part A). As in Part A, all readings and other data stored on the device will be downloaded directly from the device at the end of Part B to confirm the accuracy and frequency of the readings uploaded via the app.

At the end of Part B, a short interview will be carried out with clinicians to explore their opinions towards home monitoring and the impact it could have on their treatment schedules for patients.

Each scheduled visit allows for a +- 1-week window to allow for possible variation amongst treatment regimens.

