7.1 Qualitative assessments

In both Part A and Part B of the study, a questionnaire based on a previously validated tool²⁷ will be used to assess participants view of the monitoring device along with the process of sending in data to the secure cloud environment. This will occur as outlined above.

At the beginning and end of Part B of the study, a previously validated quality of life questionnaire will be completed²⁸.

Semi-structured, individual interviews will be performed at the end of the study period for both Part A and Part B of the study. Participants will be asked a series of open-ended questions relating to their experience of the process and all aspects of the study. An interview guide is included in the appendix. The questions will broadly assess the following parameters:

- · Overall impressions of the study
- Acceptability of StatSensor® (Part A) including calibration and operation
- · Feedback on app
- Adherence with measurements including calibration and appropriateness of frequency
- For Part A opinion on frequency of readings too many or too few
- Opinions on value of readings/trust of readings
- · Any other participant-initiated reflections or observations

All interviews should last no more than 1 hour and will take place in a private room in the hospital. Interviews will be recorded using a digital recorder and will be transcribed verbatim by the lead researcher. Recordings and transcripts will be stored in a secure environment at The Christie Hospital. The recording will be used for thematic analysis during data analysis.

At the end of Part B of the study, a clinician interview will take place, exploring:

- Overall impressions of the study
- Trust of results and future applications

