9. STATISTICAL CONSIDERATIONS AND DATA ANALYSIS

For Part A of the study, a powered sample size calculation has not taken place. In line with published recommendations³¹ 12 patients will be recruited to receive the StatSensor® to assess the general process of taking creatinine readings and sending in results via the app. Descriptive statistics will be used to summarise demographic data and clinical variables. Categorical data will be reported using frequencies and percentages. Quantitative variables will be reported using either the mean and standard deviation or the median and interquartile range depending on the distribution of the data. The standard error of the mean will also be calculated.

For Part B current powered sample size calculations estimate 30 study participants to be satisfactory. This number will be sufficient as overall creatinine levels will be used as an end point for higher statistical power as well as AKI rate. A Student's t-test and one-way ANOVA test will be used to analyse data for statistical significance.

The significance has been calculated using the assumption during standard treatment for head and neck cancer, the mean creatinine readings are 1.2 +/- 0.2 mg/dl, with closer monitoring having the potential to bring it down to 0.9+/-0.2 mg/dl based on the results of docetaxel, cisplatin, and 5-fluorouracil therapy³².

Themes from the interviews will be developed and analysed in more detail in line with published guidance on qualitative study analysis³³.

Analysis of data from this study will be in conjunction with the statistics department of the sponsor and in-house statistician support and other statistical analyses will be used as appropriate.

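### Part B quality of life: a baseline score is collected in both arms, but the protocol does not say how it is used, and the only tests named do not adjust for it

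*Protocol*

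**What the plan says.** - **Objective and outcome.** Protocol section 4, Table 2, has as a Part B secondary objective: "To assess whether home monitoring of kidney function has a positive impact on a patient's quality of life". The outcome measure is "Medical outcomes study short form 36 (SF-36) questionnaire", and the only evaluation time listed is week 6.
- **Neighbouring row.** The kidney-function row just above reads "Comparing kidney function at the beginning and end of the study" and lists weeks 1 and 6.
- **Collection.** Section 5.2 says "Participants in both groups will be asked to complete a quality of life questionnaire at baseline" and later "At the end of Part B, all participants in both groups will be asked to complete a quality of life questionnaire". Section 7.1 agrees: "At the beginning and end of Part B of the study, a previously validated quality of life questionnaire will be completed". Table 4 marks the quality-of-life assessment at baseline and at the last visit.
- **Analysis.** In its Part B paragraph, section 9 says "A Student's t-test and one-way ANOVA test will be used to analyse data for statistical significance". It closes by allowing that "other statistical analyses will be used as appropriate". Quality of life is not mentioned in section 9.
- **Size.** Section 5.2 enrols 60 patients randomised 1:1, which is 30 per arm.

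**The concern.** The baseline questionnaire is completed by every Part B participant, yet nothing says what it is for. Table 2 points to week 6 alone, although the row above it names both ends of the study. The named tests have no place for a covariate.

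With 30 per arm, much of the variation in an end-of-study score is stable difference between people, and the baseline score can remove part of it. If it is left out, or is used only by subtraction, the confidence interval for the arm difference is wider than the collected data allow, and a real effect is more easily missed.

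**Working it through.** **Plan's own figure.** There is none to reproduce. The section 9 sample size rests on creatinine. The protocol gives no standard deviation, effect size, correlation or power for quality of life.

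**Inputs from the protocol.** n = 30 per arm (section 5.2: 60 patients, 1:1).

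**Assumptions.** Two-sided 5% level (none is stated); a true difference of d = 0.5 SD; equal SD in both arms and at both times; complete data; baseline-to-end correlation r of 0.3, 0.5 or 0.7.

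**Step 1: variance of the arm difference, relative to an end-score t-test.**
- End score: 1
- Change score: 2(1 − r)
- ANCOVA on baseline: 1 − r²

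Change minus ANCOVA is 2(1 − r) − (1 − r²) = (1 − r)², which is never negative. End score minus ANCOVA is r², also never negative. So, apart from one degree of freedom, ANCOVA is at least as precise as either way of running the t-test. The change score beats the end score only if 2(1 − r) < 1, that is r > 0.5.

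| r | End score | Change | ANCOVA | Equivalent n per arm with ANCOVA, 30/(1 − r²) |
|---|---|---|---|---|
| 0.3 | 1 | 1.40 | 0.91 | 33 |
| 0.5 | 1 | 1.00 | 0.75 | 40 |
| 0.7 | 1 | 0.60 | 0.51 | 59 |

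**Step 2: power from the noncentral t distribution.** The noncentrality is d × √(n/2) / √(relative variance), with 58 degrees of freedom for the t-tests and 57 for ANCOVA. For the end score this is 0.5 × √15 = 1.936. For ANCOVA at r = 0.5 it is 1.936/√0.75 = 2.236. For change at r = 0.7 it is 1.936/√0.60 = 2.500.

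| r | End score | Change | ANCOVA |
|---|---|---|---|
| 0.3 | 47.8% | 36.3% | 51.4% |
| 0.5 | 47.8% | 47.8% | 59.4% |
| 0.7 | 47.8% | 69.1% | 76.0% |

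**Step 3: other effect sizes, at r = 0.5.** For d = 0.4, power rises from 33.2% (end score) to 42.0% (ANCOVA). For d = 0.7, it rises from 76.0% to 86.8%.

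**Step 4: is the score itself settled?** Two places conflict. Table 2 names the SF-36, but the form in Appendix 14.2 says it is adapted from the Satisfaction with Life Domains Scale. Table 2 puts the evaluation at week 6, and section 5.2 has visits at weeks B1, B3 and B6, but Table 4 puts the last assessment at week 8. The variance argument applies to whichever score and time are meant, but an analysis sentence cannot be exact until both are fixed.

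**The case against.** A reader might infer from Table 2 and the named tests that the baseline score is discarded and that only end scores are compared. The protocol does not say that, and the case against that reading is good:

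- The Table 2 column can mark when an outcome is assessed rather than which data enter it. The adherence row also says week 6, yet it covers readings from the whole period, and the Part A row says week 4 for readings over four weeks.
- A t-test can be run on change from baseline, and collection at both ends fits that use.
- The sentence naming the tests sits among the creatinine sample-size text, and section 9 leaves other analyses open.
- Covariate adjustment for a secondary endpoint is often left to a statistical analysis plan, and none is shown here.

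A reader might also infer that chance baseline imbalance biases the result. It does not: under randomisation the unadjusted comparison is unbiased and keeps its type I error.

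These points stand and narrow the concern, but they do not remove it. Table 2 is out of step with the collection schedule whatever an analysis plan says. The two routes open to the named t-test, end score and change score, are both less precise than ANCOVA across the range examined. One-way ANOVA on two arms is equivalent to the t-test and adds nothing. The open clause permits a better analysis but does not commit to one.

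**Conclusion.** The point holds as a minor one on a secondary endpoint. The protocol collects baseline quality of life in both arms, lists only week 6 for the outcome, names tests that do not adjust for baseline, and does not state how the baseline score is used.

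At 30 per arm, two-sided 5% and a 0.5 SD effect, ANCOVA gains about 4 points of power over end scores at a correlation of 0.3, 12 points at 0.5 and 28 points at 0.7. Over change scores it gains about 15, 12 and 7 points. Effect size, significance level and correlation are all assumptions. If the correlation is near 0.3, the gain over end scores is small. No stated figure in the protocol is wrong on this point, and the cost is precision only.

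**What to change.** 1. In Table 2, set the quality-of-life timepoint to baseline and end of study, in line with sections 5.2 and 7.1 and Table 4.
2. In section 9, state that the end-of-study quality-of-life score is compared between arms by ANCOVA with the baseline score as covariate, reported as an adjusted mean difference with a 95% confidence interval.
3. In the same edit, reconcile the instrument (SF-36 in Table 2; the Satisfaction with Life Domains form in Appendix 14.2) and the end visit (week 6 in Table 2; week 8 in Table 4), so that the analysis refers to one defined score at one defined time.

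Items 1 and 2 are wording only. The baseline questionnaire is already planned in both arms, so they need no added visit, patient or assessment, and the analysis gives up one degree of freedom (57 instead of 58). Item 3 needs a decision by the study team on which instrument and visit are intended.

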5. STUDY DESIGN

5.7 Part A

Twelve patients being treated for cancer with potentially nephrotoxic anti-cancer therapies (according to the judgement of the CI) will be enrolled during Part A. Following consent, each will be trained on the use of the at-home creatinine detector and provided with the device to check their creatinine at home three times per week for 4 weeks. This will be in addition to the standard care they are receiving as part of their treatment. Participants will be advised to contact their parent medical team if they have any concerns regarding their health during the study period. The participants will upload their readings to the secure cloud environment 3 times a week (Monday/Wednesday/Friday) for 4 weeks. They will be required to use their own compatible smart phone or device to access the app, and to upload the data over their own internet connection.

Part A is an evaluation of a process that has not been tested in full before, along with a device that has not been used in this setting previously. The data gathered will be run through the amended AKI algorithm to look for evidence of AKI, participants will receive confirmation that the measurement has been successfully sent. Once a week, alerts from the algorithm and creatinine readings will be reviewed by the Chief Investigator and flagged to the parent medical team if there are concerns over a reading or alert.

At the end of week A1, participants will receive a phone call to ensure they are managing with the general process of sampling and sending results through the app, and to deal with any troubleshooting issues that may have arisen. At week A1 and A4 blood and urine will be collected for

exploratory biomarker analysis, along with renal function and cystatin C. When a participant attends a clinic appointment, a creatinine reading will be taken (either by the study participant or a member of the study team) using the device, for comparison with the laboratory creatinine reading taken that day.

At the end of Part A (in line with planned appointments), the participants will complete a questionnaire assessing the acceptability of the monitoring and take part in a short interview to establish any other issues that may have arisen during the study period. At the end of Part A, all readings and other data stored on the device will be downloaded directly from the device in order to confirm the accuracy and frequency of the readings uploaded via the app. If participants would like a copy of their data at the end of Part A, this will be arranged.

Each scheduled visit allows for a +- 1-week window to allow for possible variation amongst treatment regimens.

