3.7 How this study addresses the research question

Part A of this study aims to explore whether patients who are currently receiving anti-cancer treatments are willing and able to perform intensive home monitoring of creatinine and send their results in to a cloud environment via an app to be run through an amended version of the NICE AKI algorithm to assess for evidence of AKI¹⁷. The algorithm has been amended for practicality and feasibility reasons. It is hoped that this will show the process to be convenient and acceptable to patients and clinicians and that the results are reliable. Furthermore, Part B of the study aims to show that home monitoring of creatinine will detect adverse kidney events and AKI earlier as compared to standard of care monitoring along with less overall change in kidney function in the intensively monitored group as compared with the standard of care group.

It is increasingly apparent that treatment options for this complex group of patients affected by both cancer and CKD are needed. Expanding the population of people with reduced kidney function recruited into clinical trials will be one way of meeting this clinical need.

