7.2 The System

The system described the whole process of a participant sampling their creatinine with the device and sending the result in with the smart phone application.

A smart phone application has been developed which has the capabilities to transfer the creatinine reading from the study participant to the secure cloud environment. It does not store any personal data or readings or perform any calculations. This app will be used in Part A of the study.

Using feedback from Part A of the study, the app will be developed to improve its functionality and performance.

For Part A of the study, the Nova biomedical StatSensor Xpress creatinine monitoring system has been chosen. This is a CE-Marked device for point of care testing. However, although use by patients has previously been assessed²³ ²⁹, its current intended use is by health care professionals in the hospital setting³⁰.

Part B of the study may require a device change depending upon available options at this time. If a device change is made, regulatory processes will be followed as per Section 10 - Study Governance.

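### The device reading paired with the laboratory creatinine may be taken by study staff, so the plan does not ensure that lay-operator readings are ever compared with the laboratory

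*Protocol*

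**What the plan says.** Section 5.7 (Part A) has each participant "provided with the device to check their creatinine at home three times per week for 4 weeks". Sections 3.9, 6 and 10.1 allow a carer to do this instead. For clinic appointments, section 5.7 adds that "a creatinine reading will be taken (either by the study participant or a member of the study team) using the device", and gives the purpose: "for comparison with the laboratory creatinine reading taken that day". Section 5.2 (Part B) has the same arrangement: "either by the study participant or by a member of the study team) using the device, for comparison with the laboratory reading of creatinine".

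Neither section prefers one operator, limits the use of staff, asks for the operator to be noted or separates results by operator. A carer who does the home readings is not named as a possible operator for the pair.

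Two other statements bear on this. Section 3.7 hopes that Part A will show the process to be "acceptable to patients and clinicians and that the results are reliable". Section 7.2 says of the Part A meter that "its current intended use is by health care professionals in the hospital setting".

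**The concern.** What is new in this study is lay use of the meter at home. A pair taken by staff in clinic tests the meter in professional hands, which is already its intended use. It leaves out whatever error a participant or carer adds through finger-prick technique, strip handling or timing. If staff take many of the pairs, a pooled agreement figure describes the wrong operator. If the operator was not noted, the analysis cannot recover the distinction later.

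This matters because lay readings drive the algorithm, and one of the Part B primary outcome measures in Table 2 is time to detection of AKI by that algorithm or by a clinician or laboratory reading.

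**Working it through.** The protocol gives no sample size, agreement limit or other figure for this comparison, so there is nothing to reproduce. The check has three steps.

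**1. Does any other check compare a lay reading with the laboratory?**

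| Check | Where | What it detects |
|---|---|---|
| Uploaded value against device memory | Table 2; sections 5.7 and 5.2; data management plan 2.2 | Transcription and upload errors |
| Calibration by the participant and with the hospital laboratory | Data management plan 2.2 | Meter error, not error in the user's blood sample |
| Published assessment of patient use | Cited in section 7.2 | Not a check within this trial |
| Clinic pair against same-day laboratory value | Sections 5.7 and 5.2 | Lay-user error, but only if the lay user takes the reading |

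Only the clinic pair can do it, and its operator is left open.

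**2. How many pairs are at stake?**

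- Part A inputs (section 5.7): 12 participants, 3 home readings a week for 4 weeks, scheduled blood collection at A1 and A4.
 - Home readings expected: 12 × 3 × 4 = 144.
 - Pairs at scheduled visits: 12 × 2 = 24. The text covers any clinic appointment, so 24 is the count at scheduled visits and not a ceiling.
- Part B inputs (section 5.2): 60 participants randomised 1:1, so 30 in the intensive monitoring arm; 3 readings a week for 6 weeks; visits B1, B3 and B6. Table 4 labels the visit weeks differently but also has three of them.
 - Home readings expected: 30 × 3 × 6 = 540.
 - Pairs in that arm: 30 × 3 = 90.

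With a share *f* of pairs taken by staff, lay-operated pairs = total × (1 − *f*). The protocol allows any *f* from 0 to 1:

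| *f* | Part A | Part B, intensive arm |
|---|---|---|
| 0 | 24 | 90 |
| 0.5 | 12 | 45 |
| 1 | 0 | 0 |

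**3. How far could staff readings flatter agreement? (illustration only)**

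Assume no bias, independent errors, a device-minus-laboratory SD of 8 µmol/L in professional hands and an added lay-user SD of 8 to 12 µmol/L. None of these values is in the documents. The half-width of the 95% limits of agreement is 1.96 × the SD of the difference.

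- All pairs by staff: 1.96 × 8 = 15.7.
- All pairs by lay users, added SD 8: 1.96 × √(64 + 64) = 22.2.
- All pairs by lay users, added SD 12: 1.96 × √(64 + 144) = 28.3.

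Under these assumptions a comparison made entirely by staff would report about ±16 where lay readings have about ±22 to ±28.

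**The case against.** The participant is the first-named operator, and each pair the participant takes does test lay use, at least in part. Participants are trained, may practise with staff, receive a phone call in week A1 and calibrate the meter. Part A aims at acceptability and feasibility; reliability appears as a hope in the rationale, and agreement with the laboratory is not an outcome in Table 2. An analysis split by operator could sit in a statistical analysis plan, and an operator field could already be in the workbook; neither is shown. All of this stands and limits the point to what the plan ensures. It does not remove it, because who takes the sample is a procedure that the protocol itself fixes, and it fixes it too loosely.

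Section 5.2 also sets the pair directly after a sentence about both arms, so it can be read to include control participants. They have no home operator, and a staff option is reasonable for them. The remedy has to be limited accordingly.

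A reader might infer three stronger claims that the documents do not support.

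- **That the decision to start Part B rests on this comparison.** Section 5.3 names recruitment rate and adherence, and section 5.2 conditions Part B on acceptability to patients. Section 7.2 adds that the device may change for Part B.
- **That clinic readings inflate adherence.** The measure is "Absolute number of creatinine readings received-expected vs actual". Nothing says that clinic readings are uploaded, counted as received or taken on the participant's own meter.
- **That staff would step in mainly for the weakest users.** Section 3.9 mentions fatigue and inability to take readings, but in connection with carers at home. Selective substitution by staff is plausible, not stated.

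**Conclusion.** The point holds in a limited form. As written, the plan need not yield a single lay-operated pair: 0 to 24 of the scheduled Part A pairs and 0 to 90 of those in the Part B intensive monitoring arm. It would be too strong to say that home-user readings go untested, since participant-taken pairs do count; the defect is that nothing secures them.

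The counts assume full recruitment and attendance, with one pair per scheduled visit. The share that staff would take is unknown, and the limits-of-agreement figures are illustrative; the conclusion depends on neither. Even a lay-operated pair in clinic, perhaps with staff present, is only a partial stand-in for a reading at home. The change is worth making because it is cheap and because an unrecorded operator cannot be reconstructed afterwards.

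**What to change.** - In section 5.7, and in section 5.2 for the intensive monitoring arm only, state that the usual home operator (the participant or the designated carer) takes the paired clinic reading. Staff take it only when that person is absent or cannot.
- Record the operator for each pair: participant, carer or staff.
- Base any statement on the reliability of home readings on participant and carer pairs. Show staff-taken pairs, and any control-arm pairs, separately.
- Say in section 5.2 whether the paired device reading applies to the control arm.

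The cost is a few sentences and one workbook field, a little more time in clinic, and some failed attempts. The failed attempts are themselves informative about lay use.
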